will be randomized by order and the sequence of interventions will depend on whether a previous intervention has been administered. The participant may receive a minimum of zero adherence interventions over the 3 month period to a maximum of 5 adherence interventions during the 3 month period. A similar sequence of interventions will occur if patients experience a Glucose Failure. Finally, if subjects have both an Adherence Failure and a Glucose Failure at a checkpoint, they will enter the adherence intervention pathway. They will continue on this path until they have completed all three possible interventions. After this time, if they continue to failure both adherence and glucose targets, they will enter the glucose target intervention pathway. We decided that an adherence failure trumps a glucose failure because using the Auto Mode function is critical to opening the door to achieving glucose targets.

The figure below shows the possibilities at each 2-week checkpoint.

Figure 1. Potential interventions at 2 week monthly visit

[figure not shown]

Figure 1 above graphically depicts the treatment scheme for participants in the SMART. Below, the conditions and possible scenarios are described in more detail. As a reminder, there are five checkpoints (2, 4, 6, 8, and 10 weeks). At each checkpoint, here are the possible scenarios. A = adherence; G = glucose range; and R = randomization below:

1. If 1st A failure, R to A1, A2, or A3
2. If 2nd A failure (ie., there was a previous A failure), and a history of A3, R to A1 or A2
3. If 2nd A failure, with history of (respectively) A1(A2) give A2(A1).
4. If A success, 1st G failure, R to G1,G2,G3
5. If A success, 2nd G failure, w/ history of G3, R to G1,G2
6. If A success, 2nd G failure, w/history of (respectively) G1(G2) give G2(G1).
7. All else, no treatment.

As noted above, an Adherence Failure is defined as use of Auto Mode for less than 70% of the time at a checkpoint. A Glucose Failure is defined as spending less than 65% of the time in the 70 - 180 mg/dL range at a checkpoint. Also note that the final visit at 3 months is the end of the study and no interventions are offered at that study visit.

Study Group

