The primary effect we are interested in is percent change in the amount of time spent in the target glucose range from baseline to study completion. Data from our CGM study with toddlers (NIDDK funded DP3; [name] PI) show that of the sixteen 2-6 year-olds in the study they achieve, on average, only 45% time in 70-180 mg/dL target range (standard deviation = 15%). Our hypothesized change will be a 10% improvement in time spent in target range. There is sufficient power (0.9) to detect this change in a sample size of 26. Another aspect of calculating power in this study is the actual number of participants exposed to the planned interventions after a glucose “failure.” Over 90% of the participants in our DP3 toddler study experienced a glucose failure of less than 60% time in target range. Further, the table below shows the results of glucose failures from the DirectNet cohort of toddlers using CGM (Ped Diabetes 13:301-7, 2012).

Table 1. Expected Failure Rates

| | Months | | | | | | |
|---|--------|-----|-----|-----|-----|-----|-----|
| | 0 | 1 | 2 | 3 | 4 | 5 | 6 |
| Glucose Failure (not having at least 65% of readings in the 70-180 mg/dL range) | - | 70% | 70% | 70% | 70% | 75% | 75% |

The SMART design of our proposed study allows for randomization to one of 3 conditions when there is a glucose failure (2 interventions and 1 control). Because of this, participants can contribute to more than one comparison which increases power. This makes the SMART design very efficient, particularly when examining multiple treatment strategies, which is what clinicians do in these cases. Our primary outcome will be Glucose Failure, which we expect 80-90% of participants to experience. With 27 participants available for randomization after a Glucose Failure and each subject assigned at least once to each of the three intervention groups, there is only 73% power to detect a difference of 10% change in time spent in range for a given intervention. In other words, going from 45% time spent in range at baseline to 55% time spent in range at study completion; an outcome of 10% change. Thus, while the percent change in the sample from baseline to the end of the continuation phase does appear to be adequately powered for the group, the testing of individual interventions is underpowered. We will proceed with caution when estimating likely effect sizes for each intervention based on the results of the planned analyses.

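### The 73% power for a single glucose intervention assumes an exposure that the numbered checkpoint rules cannot produce, and it does not follow from the stated inputs

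*Combined protocol and SAP*

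**What the plan says.** Biostatistics and Data Analysis gives one power figure for individual interventions. Its premise is "With 27 participants available for randomization after a Glucose Failure and each subject assigned at least once to each of the three intervention groups", and its result is that "there is only 73% power to detect a difference of 10% change in time spent in range for a given intervention". The next sentence explains the 10%: "In other words, going from 45% time spent in range at baseline to 55% time spent in range at study completion". The paragraph ends by conceding that "the testing of individual interventions is underpowered".

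The numbered checkpoint rules under Study Procedures set who receives what after a glucose failure:

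- Rule 4: "If A success, 1st G failure, R to G1,G2,G3".
- Rule 5: "If A success, 2nd G failure, w/ history of G3, R to G1,G2".
- Rule 6: "If A success, 2nd G failure, w/history of (respectively) G1(G2) give G2(G1" (closing bracket omitted here).
- Rule 7: no treatment in any other case.

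The narrative just before these rules reads differently. It allows up to five adherence interventions, keeps a family that fails both targets on the adherence path until all three have been given, and says glucose failures are handled in a similar way.

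**The concern.** The power statement needs every child to pass through all three glucose conditions. Under the numbered rules, a child who starts on G1 or G2 can never reach G3. The 73% also looked hard to obtain from the difference, SD and sample size printed beside it.

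The stated objective is to find out which interventions work best, and the Synopsis promises a comparison of each with the minimal intervention. If far fewer children enter one condition than the paragraph assumes, contrasts with that condition are much weaker than 73% suggests. The results are also meant to inform the sample size of a larger trial, for which realistic counts per condition matter.

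**Working it through.** **Inputs.** From Biostatistics and Data Analysis: difference 10 points, SD 15 (the SD of the level of time in range; no SD of change is given), 27 available, three glucose conditions. From Sample Size in the Synopsis: alpha 0.05. Assumed here: two-sided testing, 1:1:1 allocation, all 27 reaching rule 4 with adherence success, and continued failure at later checkpoints. Adherence failures take priority and could lower the counts.

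**Formulas.** Power is from the noncentral t distribution. One-sample: noncentrality (10/SD)·√n. Two-sample: (10/SD)/√(1/n₁ + 1/n₂).

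**The plan's whole-group figure.** n = 26, SD 15: 0.667 × √26 = 3.40, power 90.4%. The stated 0.9 is reproduced by a one-sample t test.

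**The 73% with the same inputs.**

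- 27 versus 27: 0.667/√(2/27) = 2.45, power 67% (t) or 69% (normal).
- One-sample, n = 27: 0.667 × √27 = 3.46, power 92%.
- 30 versus 30: 0.667/√(2/30) = 2.58, power 72% (t) or 73% (normal).
- Paired, n = 27: 73% needs a correlation of about 0.16. The SD of the difference is then 15·√(2 × 0.84) = 19.4. If that correlation also applied to the whole-group test, n = 26 would give 71%, not 90%.
- One-sided 0.05, 27 versus 27: 78%.

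**Exposure counts under rules 4–7, N = 27.** Nine children start in each condition. Rule 2 glosses a second failure: "If 2nd A failure (ie., there was a previous A failure), and a history of A3, R to A1 or A2". By analogy, the glucose rules can be read in two ways.

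- Strict (the second failure only): G1 = 9 + 9 + 4.5 = 22.5; G2 the same; G3 = 9. Nobody receives all three.
- Loose (any later failure): G1 = 27, G2 = 27, G3 = 9. Only the 9 who start on G3 can receive all three.

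If 70% fail at each checkpoint (the monthly rate in Table 1, assumed per checkpoint and independent), G3 stays at 9. G1 and G2 are then about 22 (strict) or 26 (loose).

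**Power on those counts.** Difference 10, two-sided 0.05. Groups are treated as independent, although recipients overlap. SD of change = 15·√(2(1 − ρ)), where ρ is the within-child correlation: 17.7, 15.0 and 11.6 at ρ = 0.3, 0.5 and 0.7.

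| Contrast | n | ρ = 0.3 | SD 15 (ρ = 0.5) | ρ = 0.7 |
|---|---|---|---|---|
| With G3, first assignment | 9 v 9 | 20% | 26% | 40% |
| With G3, strict | 22.5 v 9 | 28% | 37% | 56% |
| With G3, loose | 27 v 9 | 30% | 39% | 58% |
| G1 v G2, strict | 22.5 v 22.5 | 46% | 59% | 81% |
| G1 v G2, loose | 27 v 27 | 53% | 67% | 87% |
| Before-after, G1 or G2, strict | 22.5 | 72% | 86% | 97% |
| Before-after, G1 or G2, loose | 27 | 80% | 92% | 99% |
| Before-after, G3 | 9 | 32% | 42% | 62% |

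Example for the last row: at SD 15, (10/15) × √9 = 2.00 on 8 df gives 42%.

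**The case against.** The plan itself explains the 10% as a before-after change from 45% to 55%. On that contrast, the exposure counts from its own rules give about 86–92% for G1 or G2 at SD 15, and 72% for 22.5 recipients at a correlation of 0.3. This stands. A reader might infer that true power for an individual intervention is 26–39% and that 73% is inflated throughout. The documents do not support that, because the between-group contrast is only one of at least two that the text allows.

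The 73% can also be reached with 27 under assumptions the plan does not state: a paired correlation near 0.16, an SD of about 14.0–14.3, covariate adjustment at a correlation of about 0.3, or roughly (72%) a six-fold multiplicity adjustment of a one-sample test. So the figure is unreproducible from what is printed, not proven wrong. A reader might infer that the planners used the 30 enrolled before dropout. The number fits, but nothing in the text says so.

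The narrative under Study Procedures leans towards exposure to all three conditions, and Figure 1 is not available here. That does not remove the problem. The sentence about completing all three concerns the adherence path, and it disagrees with the numbered rules for that path as well.

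Finally, the plan calls itself a pilot, describes these tests as underpowered and promises caution. That limits the consequence, but it corrects neither the premise nor the number.

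**Conclusion.** The point holds in two parts. First, the exposure premise is incompatible with the numbered rules on either reading of a second failure. This needs no statistical assumption; only the figure of about 9 of 27 needs equal allocation and all 27 reaching rule 4. Second, 73% does not follow from the stated difference, SD, alpha and n.

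The size depends on the contrast. For every contrast involving G3, power is below 73%: 26–39% between groups (about 20–58% over correlations 0.3–0.7) and 42% before-after, at an SD of change of 15 for the central figures. G1 versus G2 is 59–67% at that SD. For a before-after test of G1 or G2 at SD 15, 73% is not an overstatement. These are simple t-test figures; the planned growth models are not modelled.

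The documents do not say which of G1–G3 is the minimal condition. Since the three are two interventions and one control, at least one active-versus-control contrast involves G3 whatever its label.

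It should be fixed, but the impact is limited. No decision rule uses the 73%, and the whole-group 0.9 and the plan's own conclusion of low power are unaffected. Confidence is high on the conflict and the failure to reproduce, and lower on any single replacement figure.

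**What to change.** - Reconcile the numbered rules and the narrative under Study Procedures with the power paragraph. This review does not say which sequence is right.
- State whether a second failure means the second only or any later one, and which of G1–G3 is the minimal condition.
- Remove the clause placing each child in all three groups unless the reconciled rules support it.
- State the contrast, the N (with dropout and failure rate each applied once), the test and sidedness, and the SD of change or within-child correlation.
- Replace the 73% with power, or a detectable difference, computed from the exposure counts those rules produce. If both between-group and before-after contrasts are intended, report them side by side and state how overlap between groups was handled.

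The cost is protocol wording and one recalculation. No participants are added, though the stated figure may become less favourable.

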This adaptive study design employs the possibility of subsequent randomizations if pre-designated targets are not reached. All participants will be ages 2-6 years old and in the continuation phase of the Medtronic CEP 302 Trial using the Medtronic MiniMed 670G pump with Guardian 3 sensor. All subjects will receive the same standardized education on using the pump with hybrid closed loop capabilities and continuous glucose monitoring (CGM) during the initial Medtronic CEP 302 trial phase. A review session will also take place as they enter the extension phase of the study which is the beginning of this study. Their uploaded data will be reviewed every two weeks and if they are not meeting adherence ($\geq 70\%$ of the time in closed-loop) and glycemic target goals ($\geq 65\%$ of sensor values between 70 - 180 mg/dL), they will be randomized to six interventions: 1) reduce psychological distress, 2) reduce worries about hypoglycemia, 3) education and understanding of developmental and technologic demands for using hybrid closed loop this age group, 4) understanding and modification of carbohydrate to insulin ratios, set point and in depth nutritional education, and interventions 5) and 6) will be minimal interventions with a text message providing information on how they are doing at meeting their targets. All these interventions will be compared to a minimal intervention (text of their results compared to target goals). We will examine group differences over a 3-month period on health and psychological outcomes at baseline and after three months.

Objectives: The objective of this study is to assess several remote interventions with families in the extension phase of the 670G toddler study to determine which interventions are most effective in improving their time in target (70-180 mg/dl) and their adherence in maintaining closed-loop control (at least 70% of the time in closed-loop).

Sample Size:

- We anticipate enrolling at least 4 subjects at each of the current sites, and would like to expand the number of sites to include Yale, and the University of South Florida. Each of these sites is scheduled to enroll at least 4 toddlers, and some will enroll up to 8. We therefore anticipate being able to enroll at least 30 subjects. A sample size of 26 subjects should allow for a statistically significant result with a power of 0.9 and a p of 0.05. Enrollment of 30 subjects would allow for a 10% drop out rate. See Biostatistics and Data Analysis section.

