Our primary outcome will be tested in two ways. First, by using latent growth curve models to compare change in response to treatment strategies, we can examine outcomes from checkpoint to checkpoint. For example, we can test percent change in time spent in range from week 2 to 4 and determine which intervention is associated with promotion of change during that time period. Because more than three time points are available in this study, nonlinear trajectories will also be examined. Second, we will also examine the treatment effect using separate individual trajectory models for the primary outcome across the entire 3 months of the study. These analyses will inform more precise sample size considerations based on observed effect sizes for a larger efficacy trial conducted after this proposed research is completed.

Study population

The patient population is children with type 1 diabetes and their parents who are actively enrolled in the IRB and FDA approved Medtronic CEP302 study (IDE# G150247, NCT02660827) . Parents (18 years and older) will provide informed consent for their own participation and parental permission for their child to participate. We will enroll and randomize 40 families.

Eligibility criteria

To be eligible for the study, a child must meet the following criteria:

1. Enrollment in the continuation phase of the Medtronic CEP 302 study
Ages 2 to <7.0 years of age

Expected duration of the study participation

Duration of study participation is expected to be three months.

Start Date: As early as September, 2017.

End Date: As late as September, 2018

Adverse Event Reporting and Safety Monitoring

Overview of Safety Monitoring

All participants will have glucose data reviewed at planned intervals for study adherence. All of the other medical monitoring of these subjects are done as part of the IRB and FDA approved Medtronic CEP302 study (IDE# G150247, NCT02660827)

Definition of Adverse Event

Adverse event reporting and definitions for these research participants will be defined and carried out via the IRB and FDA approved Medtronic CEP302 study (IDE# G150247, NCT02660827), as these encompass all the inherent risks of Type 1 Diabetes, insulin pump use, and continuous glucose sensor use.

Recording of adverse events

Reportable adverse events and serious adverse events are defined and carried out in accordance with the IRB and FDA approved Medtronic CEP302 study (IDE# G150247, NCT02660827)

Data and safety monitoring

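### The 3-month treatment effect cannot be read as the effect of a single intervention, because the failure rules switch most children before week 12

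*Combined protocol and SAP*

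**What the plan says.** The Synopsis sets out to find which interventions work best and states: "All these interventions will be compared to a minimal intervention".

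Biostatistics and Data Analysis gives two tests of the primary outcome. The first uses latent growth curve models to follow change between successive checkpoints, with weeks 2 to 4 as its example. The second reads: "we will also examine the treatment effect using separate individual trajectory models for the primary outcome across the entire 3 months of the study". The power paragraph of the same section illustrates a given intervention's effect as "going from 45% time spent in range at baseline to 55% time spent in range at study completion". The observed effect sizes are to inform the size of a later efficacy trial.

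The numbered rules in Study Procedures govern what happens at weeks 2, 4, 6, 8 and 10. A first glucose failure leads to randomisation among G1, G2 and G3. After that:
- Rule 5: "If A success, 2nd G failure, w/ history of G3, R to G1,G2".
- Rule 6: "If A success, 2nd G failure, w/history of (respectively) G1(G2) give G2(G1", that is, the other active intervention, without randomisation.

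Rules 1-3 have the same structure for adherence. No rule keeps a failing child on the first condition, and none gives G3 after G1 or G2.

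The plan does not define the strategies embedded in these rules, a time-varying exposure, or which intervention a 3-month trajectory is credited to.

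**The concern.** A per-intervention effect read at week 12 needs children whose week-12 value reflects that intervention alone. The rules remove most of them. Children who start on the minimal condition and fail again go to an active intervention. Children who start on one active intervention and fail again receive the other. The interventions are education and skills, so the first can carry over into the second.

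The threshold adds to this. Success needs 65% in range, while the hypothesised result is 55%. A child who gains exactly what the plan hopes for will usually still count as a failure and be switched.

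At stake are the effect sizes passed to the later trial. Read as single-intervention effects, 3-month contrasts could make a working intervention look null, or present the effect of two interventions as the effect of one. More children would not cure this, because it is bias and not imprecision.

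**Working it through.** **The plan's own figure.** Inputs are in the Synopsis and Biostatistics sections: "A sample size of 26 subjects should allow for a statistically significant result with a power of 0.9 and a p of 0.05", "Our hypothesized change will be a 10% improvement in time spent in target range", SD 15 points. A paired t-test with change 10, SD of change 15, two-sided 0.05 and n = 26 has power 0.904, which reproduces 0.90. For dropout ("Enrollment of 30 subjects would allow for a 10% drop out rate"), 26 / (1 - 0.10) = 28.9, so 29, and 30 covers it. This test concerns the whole group, so switching between interventions does not affect it.

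**Does a successful intervention avoid a switch?** Inputs: mean 45, SD 15, threshold 65; normality assumed.
- Before any gain: P(below 65) = Φ((65 - 45)/15) = Φ(1.33) = 0.909.
- After the hypothesised gain: P(below 65) = Φ((65 - 55)/15) = Φ(0.67) = 0.748.
- Ratio: 0.748 / 0.909 = 0.82. About 82% of children who failed at 45% would still be failures after gaining 10 points.

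**Switching at the plan's expected failure rate.** Table 1 gives 70% in months 1-3. Applied to each of the five checkpoints, with independence (both assumptions):
- P(at least one failure) = 1 - 0.3^5 = 0.9976.
- P(exactly one) = 5 × 0.7 × 0.3^4 = 0.0284.
- P(switched, given any failure) = 1 - 0.0284/0.9976 = 0.972.
- Of the plan's 27 randomised children, 27 × 0.0284/0.9976 = 0.8 stay on their first condition only.

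If failures persist within a child, so that 80-90% ever fail as the plan expects, 90-93% are switched. If the failure rate after the first intervention falls to 50%, 30% or 20%, then 90%, 71% or 54% are switched. Fewer than half are switched only below about 18%.

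**Effect on the contrast.** Rules 4-6 were simulated with 400,000 children and five checkpoints. Assumptions: 1:1:1 first allocation, G3 is the minimal condition and has no effect, every child an adherence success, between-child SD 15, within-child SD 4-8 points, and a lasting 10-point effect of an active intervention.

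| Starting mean | G3-first given an active intervention | G1-first also given G2 | Week-12 G1 minus G3, second intervention adds nothing |
|---|---|---|---|
| 45% | 97-98% | 87-91% | 0.2-0.4 points |
| 60% | 88-92% | about 65% | 0.8-1.2 points |
| 65% | 82-89% | 55-59% | up to about 1.8 points |

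At the next checkpoint after first randomisation the G1-versus-G3 difference is 10 points throughout. If effects add, the week-12 difference is 6.6-9.2 points, but it then compares mostly two interventions with one.

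**Randomised or fixed.** About 55-65% of second-line glucose assignments are the fixed switches of rule 6, which have no randomised alternative and no minimal comparator.

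**The case against.** The strongest case on the other side has five parts.

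- *The plan already tests checkpoint to checkpoint.* This stands. A reader might infer that every intervention effect is read over 3 months; the first test shows otherwise and is the right vehicle. It does not, however, separate randomised first assignments from the fixed switches of rules 3 and 6.
- *Switching is deliberate in a SMART.* This stands. Grouped by first assignment, the trial keeps a valid randomised comparison of strategies to week 12. A reader might infer that the design leaves no valid comparison, or that no child stays on the first condition; neither is supported. A few children do stay, but they are selected by outcome or by late first failure. The gap is that the 3-month test is not said to estimate strategies, while the power paragraph speaks of a given intervention at study completion.
- *The lead figures are favourable to the concern.* Partly right. The 45% mean comes from a CGM study, and Study Procedures are for children already using closed loop, so starting means up to 65% are shown. Adherence failures, whose rate is not given, take precedence and lower glucose switching. With an assumed 30-50% rate and mean 45%, G3-first crossover falls to 78-88% and G1-first to 70-79%, still a clear majority.
- *The difference need not vanish.* Right. A near-zero week-12 contrast requires that a second active intervention add nothing, and the documents do not say whether it does.
- *It is a pilot that admits low power for individual interventions.* Right, and it lowers the severity. But that caveat concerns precision and does not mention switching.

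**Conclusion.** The point holds for the 3-month treatment effect and for the power paragraph's effect of a given intervention at study completion. Neither can be read as the effect of a single intervention.

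Under the simulation's assumptions and starting means of 45-65%, about 82-98% of G3-first children receive an active intervention and about 55-91% of G1-first children also receive G2. A 10-point difference at the next checkpoint becomes about 0.2-1.8 points at week 12, or about 7-9 points of a different quantity if effects add. That G3 and A3 are the minimal condition is inferred from the rules and from the plan's count of two interventions and one control; the figure is not shown.

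The whole-group change, the checkpoint test in principle, and a strategy comparison by first assignment are not undermined. Severity: should-fix.

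**What to change.** Reword Biostatistics and Data Analysis:

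1. Make the checkpoint test the per-intervention estimate: the difference from minimal intervention, within the same pathway, in change from the first randomising checkpoint to the next checkpoint.
2. Use rule 2 and rule 5 assignments only to compare A1 with A2, and G1 with G2, after minimal intervention. Report rule 3 and rule 6 assignments descriptively.
3. Fit the 3-month trajectory model by first randomised assignment and label it a comparison of strategies (for example, start with G1, then G2 if failing again), not of single interventions.
4. Take the later trial's per-intervention effect sizes from item 1, not item 3.

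Also reconcile the power paragraph's premise that every child receives all three glucose conditions with rules 4-7, under which a child who starts on G1 or G2 never receives G3.

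The cost is wording only, with no change to visits, patients or assignments. The downside is that the single-intervention effect becomes a 2-week effect, with the sessions themselves taking up one of those weeks, and rests on fewer observations. With 1:1:1 allocation, 27/3 = 9 children start on each condition, and 9 against 9 has power of only about 0.26 for 10 points with SD 15 (two-sided t-test). The estimates should therefore be reported with intervals, in keeping with the plan's own caution.
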